#### 8.2.1. Rabies Virus Neutralizing Antibodies (VNA)

Results from the RFFIT assay will be reported in IU/mL, with a typical range of 1-15 IU/mL. Results beyond 15 IU/mL will require dilution and retesting. The lower limit of quantification for the RFFIT assay is 0.1 IU/mL; values below the LLOQ will be imputed as 1/2 the LLOQ, or 0.05 IU/mL.

Serum samples for rabies VNA will be collected prior to vaccination (Day 1) and on Day 8, Day 15, Day 22, Day 29, Day 91, Day 181, and Day 381.

For each sample time point (and peak post-vaccination value), the GMT and 95% CI of the rabies VNA results will be analyzed and presented as described above, including post-baseline seroconversion rates and exact Clopper-Pearson 95% CI for the mITT and PP populations ([Table 21](#) and [Table 22](#), respectively).

Graphical displays of the reverse cumulative distribution curves, by time point and vaccine group, will be presented for the mITT and PP populations ([Figure 2](#) and [Figure 3](#), respectively). Similarly, graphical box-and-whisker plots will be presented for rabies VNA titers ([Figure 4](#) and [Figure 5](#), respectively) and for the percent seroconversion rate and 95% CIs ([Figure 6](#) and [Figure 7](#), respectively).

The pair-wise differences in seroconversion rates will be computed at each post-vaccination visit, with corresponding 95% CI computed via the Miettinen and Nurminen score method, for the mITT and PP populations ([Table 23](#) and [Table 24](#), respectively). Pair-wise differences and 95% CIs will be based on standard 2 x 2 table analyses and estimated using PROC FREQ and the RISKDIFF option in SAS. See pseudo code below.

```
PROC FREQ DATA=aa;
  TABLE Grp*Response / RISKDIFF(CLTYPE=MN);
```

*OUTPUT OUT=bb RISKDIFF;  
RUN;*

A listing of all rabies VNA titers will be presented in [Listing 9](#).

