### 3.2.2. Secondary

- Proportion of subjects seroconverting to rabies virus at each antibody time point (seroconversion is defined as VNA concentration  $\geq 0.5$  IU/mL), in each vaccination group and overall.
- GMT (as measured by rabies VNA using a standard, WHO-approved, RFFIT) at each antibody time point within each vaccination group.
- Peak GMT (as measured by rabies VNA using a standard, WHO-approved, RFFIT; peak GMT is defined as highest GMT measured across all post-vaccination antibody time points) within each vaccination group.

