## 3.3. Study Definitions and Derived Variables

Seroconversion is defined as a VNA concentration  $\geq 0.5$  IU/mL. Peak GMT is defined as the highest GMT measured across all post-vaccination antibody time points per subject.

The baseline value will be defined as the last value obtained prior to the first vaccination.

Vaccination group is defined as the four vaccine and dose combinations:

- Low Dose ChAd155-RG
- High Dose ChAd155-RG (x1)
- High Dose ChAd155-RG (x2)
- RABAVERT

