## 4.5. Immunogenicity and Safety Variables

For additional details on study procedures and evaluations by study visits/days, see [Table 2](#).

Safety will be assessed by the frequency and/or severity of:

- Solicited injection site and systemic reactogenicity events from the time of each vaccination through Day 7 after each vaccination, overall and in each vaccination group.
- Serious adverse events (SAEs) considered study vaccine-related and reported at any time after the first vaccination through the end of this trial, overall and in each vaccination group.
- Vaccine-related lab AEs through study Day 22, overall and in each vaccination group.
- Unsolicited vaccine-related AEs from the time of the first vaccination through Day 28 after the last vaccination, overall and in each vaccination group.
- New onset chronic medical conditions at any time after the first vaccination and through the end of this trial, overall and in each vaccination group.
- Local, systemic or lab toxicities after any vaccination, overall and in each vaccination group.
- Local reactogenicity through Day 7 after any vaccination, overall and in each vaccination group.
- Any SAEs, overall and in each vaccination group.

Immunogenicity will be assessed by:

- Proportion of subjects seroconverting to rabies virus at each antibody time point (seroconversion is defined as VNA concentration  $\geq 0.5$  IU/mL), in each vaccination group and overall.
- GMT (as measured by rabies VNA using a standard, WHO-approved, RFFIT) at each antibody time point within each vaccination group.
- Peak GMT (as measured by rabies VNA using a standard, WHO-approved, RFFIT; peak GMT is defined as the geometric mean of the highest titer per subject across all post-vaccination antibody time points) within each vaccination group.
- Frequencies of circulating T cell responses against RG by ex vivo IFN-ELISpot.
- Characteristics of circulating CD4 and CD8 T cell responses against RG by multiparameter ICS.
- Magnitude and durability of RG-specific memory B cells by ELISpot.
- GMT to ChAd155 vector at one month after first vaccination.

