#### 6.3.2. Per Protocol Population

The per protocol (PP) population includes all subjects in the mITT subset with the following exclusions:

- Data from all available visits for subjects found to be ineligible at baseline, according to the inclusion and exclusion criteria at the time of the subject's enrollment.
- Data from subjects who have a baseline rabies VNA concentration  $\geq 0.5$  IU/mL (for the immunogenicity analyses).
- Data from all visits subsequent to the following, such as:
  - Study withdrawal or treatment discontinuation
  - Any study vaccination dose received out of window
  - Receipt of non-study licensed live vaccine within 30 days before or after each study vaccination
  - Receipt of non-study licensed inactivated vaccine within 14 days before or after each study vaccination
  - Receipt of immunosuppressive therapy (e.g., corticosteroids) within 30 days before or after each study vaccination

- Receipt of chloroquine or hydroxychloroquine
- Data from any visit that occurs out of window, as defined in [Table 2](#) “Window for each study visit”.

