**Table 15: Analysis Populations by Vaccination Group (*continued*)**

Analysis Populations	Reason Subjects Excluded	Low Dose ChAd155-RG (N=X)		High Dose ChAd155-RG (x1) (N=X)		High Dose ChAd155-RG (x2) (N=X)		RABAVERT (N=X)		All Subjects (N=X)	
		n	%	n	%	n	%	n	%	n	%
	Visit occurs out of window										
	Study withdrawal a,b										
	Treatment discontinuation b										
	Study vaccination dose received out of window b										
	Receipt of non-study licensed live vaccine within 30 days before or after study vaccination b										
	Receipt of non-study licensed inactivated vaccine within 14 days before or after study vaccination b										
	Receipt of immunosuppressive therapy (e.g., corticosteroids) within 30 days before or after study vaccination b										
	Receipt of chloroquine or hydroxychloroquine b										
	Repeat Day 8 for:										
	Prior to or at Day 15 visit:										
	Prior to or at Day 22 visit:										
	Prior to or at Day 29 visit:										
	Prior to or at Day 91 visit:										
	Prior to or at Day 181 visit:										

Note: N=Number of subjects enrolled; n=number of subjects meeting the criteria.

aSubjects visits may be included in the PP population up to study withdrawal.bSubjects are excluded from per protocol analyses at all timepoints subsequent to the occurrence of the protocol deviation. Subjects are summarized in this table at all affected timepoints.

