**Figure 5: Rabies VNA Titer Over Time by Vaccination Group – Per Protocol Population**

**Figure 6: Rabies VNA Geometric Mean Titer and 95% CI Over Time Point by Vaccination Group - mITT Population\***

Implementation note: an example figure is shown below. The x-axis will include all study days for which RFFIT titer data is available, along with an “Any Time” at end of x-axis that represents the peak titers for each subject across all post-baseline visits. Different colors and symbols will be used for each study arm representing each individual titer value. The GMT will be represented as a black diamond and 95% CIs by black error bars. The y-axis label should be “RFFIT Geometric Mean Titer (IU/mL)” and the x-axis label should be “Study Visit Day”. A black dotted reference line will be drawn to represent the LLOQ of the RFFIT assay and a grey dashed reference line will represent the seroconversion titer limit of 0.5 IU/mL. “All High Dose” study arm data will be included but only up to Day 22.

[figure not shown]
[figure not shown]

Figure with Similar Format:

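### The per-protocol peak GMT and any-time seroconversion can take a Day 8 or Day 15 titre as the peak of a subject whose data are cut off before Day 29

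*SAP*

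**What the plan says.** SAP 8.2.1 sets the analysis for the mITT and PP populations: "For each sample time point (and peak post-vaccination value), the GMT and 95% CI of the rabies VNA results will be analyzed".

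One exclusion in SAP 6.3.2 opens with "Data from all visits subsequent to the following, such as", and the list under it includes "Any study vaccination dose received out of window" as well as withdrawal and discontinuation of treatment. A separate item removes any single visit that is itself out of window. SAP Table 15 confirms that exclusion runs forward in time only: footnote b applies it to time points after the deviation, and footnote a states "Subjects visits may be included in the PP population up to study withdrawal".

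SAP 4.5 makes the peak a subject-level maximum: "peak GMT is defined as the geometric mean of the highest titer per subject across all post-vaccination antibody time points". SAP 3.3 leans the same way: "Peak GMT is defined as the highest GMT measured across all post-vaccination antibody time points per subject". The note to Figure 6, whose format Figure 7 reuses for PP, adds an any-time position that "represents the peak titers for each subject across all post-baseline visits". Figures 8 and 9 show the proportion of subjects who ever seroconverted. The secondary endpoint in SAP 3.2.2 (and protocol 3.2.2) reads differently, at group level: "peak GMT is defined as highest GMT measured across all post-vaccination antibody time points) within each vaccination group".

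Table 22 (PP) reuses the Table 21 layout, which ends in a peak row. Removed values are not imputed (SAP 6.5). Nothing states which visits a subject must still have to count in the PP peak or any-time rows, and Table 15 has no entry for them. Figure numbers here follow SAP Appendix 2; the text of 8.2.1 numbers the seroconversion plots differently.

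**The concern.** A by-visit PP row handles a truncated subject correctly, because the subject simply drops out of later rows. A maximum over visits does not. The subject stays in the row and contributes the highest of the few early titres left. A maximum over a subset of visits can equal the maximum over all visits but never exceed it, so the cut-off lowers that subject's peak or leaves it unchanged.

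PP rows are read as the response to the regimen as planned. Here they could mix full-course peaks with titres taken before the course was complete. The mITT set keeps the later visits after a dosing deviation, so a gap between mITT and PP could arise from this construction alone and be read as an effect of adherence.

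**Working it through.** **1. Which visits remain.** Vaccination visits have a +2 day window (protocol 7.4, SAP Table 2), and samples on those days are drawn before the injection (Table 21, note a). Assume a late injection also puts its own visit out of window.
- Late Day 8 injection: no post-baseline PP value is left, so the subject does not enter the peak row.
- Late Day 15 injection: only Day 8 is left.
- Late Day 22 injection: Days 8 and 15 are left.
- Cut-off after Day 29: the samples from Day 8 to Day 29 stay.

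Against SAP Table 1, the Day 15 sample precedes the second active dose in Group C and the third in Group D. In Groups A and B the injections on Days 8, 15 and 22 are placebo. SAP 6.3.2 does not exempt placebo, so a late placebo truncates those subjects too.

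**2. The plan's own figures.** The documents give no figure for the peak endpoint. The nearest is SAP Table 5, the confidence intervals for seroconversion. Clopper-Pearson limits with x = N × rate reproduce all 12 intervals. Examples: N=12 at 90% gives 59.4% to 99.6%, printed as (59%, 100%); N=14 at 100% gives 76.8% to 100%, printed as (77%, 100%).

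**3. Effect on the peak GMT.** Let n be the subjects in the row, k the number truncated, T the peak of the others and L the retained early titre. Then

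GMT = (T^(n−k) × L^k)^(1/n) = T × (L/T)^(k/n).

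Group sizes are 10 (C), 12 (D) and 14 (A, B), from SAP 5. The lowest possible L is 0.05 IU/mL, half the LLOQ (SAP 8.2.1). T, and L = 1.0 for a Day 15 type of value, are assumptions. Example: 10 × (0.05/10)^(1/10) = 5.89. The multiplier on the GMT for k = 1 is:

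| L (IU/mL) | n | T=2 | T=5 | T=10 | T=15 |
|---|---|---|---|---|---|
| 0.05 | 10 | 0.69 | 0.63 | 0.59 | 0.57 |
| 0.05 | 12 | 0.74 | 0.68 | 0.64 | 0.62 |
| 0.05 | 14 | 0.77 | 0.72 | 0.68 | 0.67 |
| 1.0 | 10 | 0.93 | 0.85 | 0.79 | 0.76 |
| 1.0 | 12 | 0.94 | 0.87 | 0.83 | 0.80 |
| 1.0 | 14 | 0.95 | 0.89 | 0.85 | 0.82 |

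The loss is 1 − 0.77 = 23% to 1 − 0.57 = 43% at L = 0.05, and 1 − 0.95 = 5% to 1 − 0.76 = 24% at L = 1.0.

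**4. Interval for the GMT.** Take nine subjects with GMT 10 and an assumed log10 SD of 0.3. The t interval is 5.88 to 17.01. Adding one subject at 0.05 gives 5.89 (1.63 to 21.30).

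**5. Any-time seroconversion.** Assume all other subjects are positive and the truncated one is below 0.5 IU/mL. For n=14 the row shows 13/14 = 93% (66% to 100%), against 13/13 = 100% (75% to 100%) if that subject is left out. For n=10 it shows 9/10 = 90% (55% to 100%), against 9/9 = 100% (66% to 100%). The drop is 7 to 10 points. A retained titre of 1.0 is above 0.5, so nothing changes.

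**6. When PP is run.** SAP 8.2 adds PP only if more than 5% of subjects are affected: 0.05 × 50 = 2.5, so at least 3. Not every such exclusion is an early cut-off.

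**The case against.** Several points on the other side stand.

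- **Definition.** Under the group-level wording of the secondary endpoint, a truncated subject leaves the later time points and no early titre becomes a peak. The GMT part is therefore conditional on which wording governs. SAP 4.5 and the figure notes use subject maxima, and any-time seroconversion does not depend on this wording.
- **Day 15.** A reader might infer that a Day 15 titre is also pre-response. The documents do not support that. The only kinetics they give, from non-human primates (protocol 2.1), put all 10 ChAd155-RG animals above the protective threshold by two weeks, with peaks between weeks 2 and 4. Day 15 is pre-peak at most. Day 8 is likely to be largely pre-response, but no titres from the first week are given.
- **Arms.** A reader might infer that Groups C and D suffer most. This is not shown: late placebos truncate A and B as well, and B and C have had identical vaccine when the Day 15 sample is drawn.
- **Frequency.** No rate of early cut-off can be derived. Protocol 5.3.4 rules out exceptions to the dose schedule, while 9.5 allows out-of-window dosing after fever or illness with permission. Those two passages need reconciling.
- **Disclosure.** The layout prints n in each row, Table 15 counts exclusions by visit and reason, and Listings 5 and 9 show excluded visits and titres. A careful reader could trace the problem, but the n of the peak row would still count the truncated subject.
- **Stakes.** mITT is the main immunogenicity set, no hypothesis is tested, and the pairwise differences in Tables 23 and 24 have no peak or any-time column.

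None of this supplies the missing rule.

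**Conclusion.** The point holds. Followed as written, with the peak as a subject maximum, the plan can enter a Day 8 or Day 15 titre as a per-protocol peak, in any arm. It reaches only the PP peak and any-time rows and their comparison with mITT.

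The losses in the working are illustrations for a single truncated subject, not forecasts. They rest on assumed titres, on all other subjects sharing one peak value, and on all enrolled subjects being in the row. The loss of about 41% at n=10 and T=10 should not be read as typical, because it combines the smallest arm with the lowest titre a subject can carry. The mITT peak has a similar weakness for early dropouts, but there the later data do not exist, whereas in PP the plan removes them.

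**What to change.** In SAP 8.2.1, and in the notes to Table 22 and Figures 5, 7 and 9, restrict the PP peak and any-time rows to subjects whose PP data are not cut off before Day 29. State that:
- one out-of-window visit alone does not remove a subject from these rows;
- the rule applies whatever the observed titre, which matters because group-level results are seen at the interim (SAP 6.6);
- n for these rows is the number of subjects meeting the rule.

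Requiring valid samples at all of Days 15, 22 and 29 would be too strict, since it drops a subject who missed a single window. Leave the by-visit rows and the mITT tables unchanged.

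Separately, align the peak GMT wording in protocol 3.2.2 and SAP 3.2.2 with the per-subject definition in SAP 4.5.

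The cost is a short text change and one programming filter. The downside is a smaller n in the PP peak and any-time rows.

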2. BACKGROUND INFORMATION AND SCIENTIFIC RATIONALE

2.1. Background Information

Rabies is an acute, progressive viral encephalitis caused by neurotropic single-stranded RNA viruses (genus *Lyssavirus*, family *Rhabdoviridae*). This zoonotic infection is acquired after exposure to the saliva of infected domestic or wild mammals and is almost invariably fatal. Rabies is estimated to cause more than 50,000 deaths annually, mostly in Asia and Africa, but the true disease burden is likely higher due to underreporting and lack of confirmatory testing in many endemic regions.^{1,2}

Highly effective, inactivated viral vaccines against rabies have been available for use as pre-exposure prophylaxis (PrEP) or post-exposure prophylaxis (PEP) for decades. In the US, two vaccine formulations are currently available, a purified chick embryo cell vaccine (PCECV; RabAvert, GSK Vaccines), and a human diploid cell vaccine (HDCV; Imodex, Sanofi Pasteur).³ ⁴ It is recommended that both vaccines be administered in a three-dose series (Days 0, 7, and 21 or 28)³ for PrEP, and a four-dose series (Days 0, 3, 7, and 14; a fifth dose on Day 28 is recommended for immunocompromised individuals) for PEP, with or without rabies immunoglobulin (RIG) depending on the severity of the exposure.⁴ Virtually all recipients of a recommended vaccine series mount a seroprotective titer of rabies VNA, defined as a post-vaccination VNA concentration ≥ 0.5 IU/mL, or complete virus neutralization at a 1:5 serum dilution, by a WHO-approved RFFIT.

Despite the existence of effective vaccines, rabies remains endemic throughout the world. This is largely because RIG and/or rabies vaccines are not readily available, especially in countries with a high animal rabies burden, and because the recommended schedule of vaccine administration is cumbersome and cost-prohibitive. Even in the US, compliance with the recommended PEP vaccine series is suboptimal; for example, in one prospective study of rabies PEP, over one-third of individuals failed to complete the PEP vaccine series at 1 month.⁵ Thus, novel vaccines against rabies that are safe, tolerable, economical, and as immunogenic as current formulations, and that can be administered for PrEP in one dose, and for PEP in one or two doses, are urgently needed.

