3.1.3. Exploratory (if applicable)

- Quantification of circulating T-cell responses against RG by ex vivo IFN-gamma ELISpot.
- Characterization of circulating CD4 and CD8 T-cell responses against RG at peak time point by multiparameter ICS.
- Comparison of durability of immune response to ChAd155-RG and RABAVERT at approximately 3, 6, and 12 months after first dose of vaccine by each treatment arm tested.
- Measurement of RG-specific memory B cells by ELISpot.
- Measurement of an antibody response to the vaccine vector (ChAd155).

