11. STATISTICAL CONSIDERATIONS

11.1. Study Hypotheses

There are two primary objectives for this trial: to assess the safety, tolerability, and reactogenicity of one dose of ChAd155-RG at 5×10^{10} vp per dose, or one or two doses of ChAd155-RG at 1×10^{11} vp per dose; and to compare the safety, tolerability, and reactogenicity of one or two doses of ChAd155-RG with three doses of RABAVERT. A secondary goal is to assess serum rabies VNA levels by a standard, WHO-approved, RFFIT, as assessed by immune response kinetics (through 12 months after the first dose of vaccination), seroconversion rates, and peak GMT. Also of interest are innate T cell and B cell responses, as well as ELISA binding antibodies. This trial, like other Phase I trials, is exploratory rather than confirmatory, and was not designed to test a formal null hypothesis.

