## 2.1. Purpose of the Analyses

These analyses will assess the immunogenicity and safety of ChAd155-RG (one dose at  $5 \times 10^{10}$  vp, one dose at  $1 \times 10^{11}$  vp, and two doses at  $1 \times 10^{11}$  vp) in comparison with RABAVERT and will be included in the CSR.

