## 5. SAMPLE SIZE CONSIDERATIONS

This trial will enroll 50 subjects into four vaccination groups: Group A (N=14) will receive one dose of ChAd155-RG at the lower dosage ( $5 \times 10^{10}$ vp); Group B (N=14) will receive one dose of ChAd155-RG at the higher dosage ( $1 \times 10^{11}$ vp); Group C (N=10) will receive two doses of ChAd155-RG at the higher dosage ( $1 \times 10^{11}$ vp); and Group D (N=12) will receive three doses of RABAVERT.

The sample size of 10-14 subjects in each vaccination group is small given the early stage (Phase I) of the product's development; thus, the precision of estimates for AEs is limited. Rare AEs associated with dose level or number of doses are not demonstrable in a trial of this size; however, the probabilities of observing one or more AEs within a vaccination group given various true event rates are presented in [Table 3](#). The minimum detectable event rates for various levels of power are displayed in [Table 4](#).

This trial was not designed to formally test any hypotheses associated with the immunogenicity data. The 95% confidence intervals (CIs) for various observed seroconversion rates at various sample sizes were calculated assuming observed seroconversion rates of 90%, 95%, and 100%, as shown in [Table 5](#).

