**Table 23: Rabies VNA Pairwise Differences in Seroconversion Rates by Time Point - Modified Intent to Treat Population\***

Group 1	Group 2	Difference and 95% CI (Group 1 - Group 2) in Proportion with Seroconversion						
		Day 8 (Pre-Dose 2)	Day 15 (Pre-Dose 3)	Day 22 (Pre-Dose 4)	Day 29 (7 Days Post-Dose 4)	Day 91 (69 Days Post-Dose 4)	Day 181 (159 Days Post-Dose 4) a	Day 381 (359 Days Post-Dose 4) a
Low Dose ChAd155-RG (N=X)	Combined High Dose ChAd155-RG (N=X)	x xx - xx	x xx - xx					
Low Dose ChAd155-RG (N=X)	High Dose ChAd155-RG (x1) (N=X)							
Low Dose ChAd155-RG (N=X)	High Dose ChAd155-RG (x2) (N=X)							
Low Dose ChAd155-RG (N=X)	RABAVERT (N=X)							
Combined High Dose ChAd155-RG (N=X)	RABAVERT (N=X)							
High Dose ChAd155-RG (x1) (N=X)	RABAVERT (N=X)							
High Dose ChAd155-RG (x2) (N=X)	RABAVERT (N=X)							

Note: N = Number of subjects in the mITT Population for the appropriate group.

95% CIs of pairwise differences calculated via the Miettinen and Nurminen score method.

a Day 181 time point will not be presented in the first interim immunogenicity analysis and Day 381 time point will not be presented in either interim immunogenicity analysis.

Table with similar format:

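### The only committed between-arm VNA contrast is the seroconversion difference, which is blind to titre near 100%. GMT ratios with CIs and the missing High Dose (x1) vs (x2) row would be a cheap addition.

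*SAP*

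**What the plan says.** SAP 2.1 states that the analyses assess immunogenicity and safety of the ChAd155-RG regimens "in comparison with RABAVERT and will be included in the CSR". For rabies VNA the SAP commits to these outputs:

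- **Within arm (SAP 8.2, 8.2.1, Table 21):** GMT with a t-based 95% CI, and seroconversion rate with an exact CI, at each visit and at peak. Figures 2 to 9 plot the distributions, GMTs and rates.
- **Between arms (SAP 8.2.1, Tables 23 and 24):** "The pair-wise differences in seroconversion rates will be computed at each post-vaccination visit", with Miettinen-Nurminen 95% CIs. SAP 8.2 describes these as pair-wise by treatment arm and excludes no pair. The Table 23 shell is headed "Difference and 95% CI (Group 1 - Group 2) in Proportion with Seroconversion" and has seven rows: Low Dose vs Combined High, High (x1), High (x2) and RABAVERT; then Combined High, High (x1) and High (x2), each vs RABAVERT.
- **Exploratory:** a longitudinal regression of log titre on vaccine type, dosage and dose number. Protocol 11.4.4 says it *will* be done; SAP 8.3 says it *may* be. The shells for Tables 25 and 26 leave the format open until results are known.

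On expected response, Protocol 2.1 says of the licensed vaccines: "Virtually all recipients of a recommended vaccine series mount a seroprotective titer of rabies VNA". It also reports that all 10 macaques given ChAd155-RG were above the protective threshold by two weeks. One exploratory objective is "Comparison of durability of immune response to ChAd155-RG and RABAVERT at approximately 3, 6, and 12 months after first dose of vaccine".

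**The concern.** Seroconversion is a cut at 0.5 IU/mL. Once nearly everyone in both arms is above the cut, the difference in rates says nothing about how far above. SAP 8.2.1 gives a typical RFFIT range of 1 to 15 IU/mL, all of it above the threshold, so two arms could differ up to 15-fold inside that range and have identical seroconversion. The programme's stated need is a vaccine as immunogenic as current ones in fewer doses, and that question turns on titre as well as on the threshold.

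The missing High Dose (x1) vs (x2) row is a separate matter and needs no assumption. Groups B and C differ only in the second 1×10^11 vp dose, so this is the one pair that isolates number of doses at a fixed dosage. The SAP text promises it and the table shell leaves it out.

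**Working it through.** **Inputs.** Group sizes from SAP 5: "Group A (N=14) will receive one dose of ChAd155-RG at the lower dosage"; Group B is also 14, Group C 10, Group D 12. Threshold 0.5 IU/mL. The documents give no titre SD and no expected human GMT. I assume SD 0.3 to 0.6 log10 throughout, and a RABAVERT GMT of 10 IU/mL only where stated.

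**1. The plan's own precision figure.** At 100% observed, the exact lower limit is 0.025^(1/n): 69.2% (n=10), 73.5% (n=12), 76.8% (n=14). SAP Table 5 prints 69%, 74% and 77%, so it reproduces.

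**2. Counting pairs.** Four arms give 4×3/2 = 6 pairs. Table 23 has five of them plus two Combined High rows. The absent pair is High Dose (x1) vs (x2).

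**3. The planned contrast at its ceiling.** When every subject in both arms seroconverts, the Miettinen-Nurminen limits have a closed form. With N = n1+n2 and k_i = 1.96² × N / [(N-1) × n_i], the limits are -k1/(1+k1) and +k2/(1+k2).

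- A or B vs D (14/14 vs 12/12): k1 = 3.84×26/(25×14) = 0.285 and k2 = 3.84×26/(25×12) = 0.333, giving -22 to +25 points.
- C vs D (10/10 vs 12/12): -29 to +25 points.
- B vs C (14/14 vs 10/10): -22 to +29 points.

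No titre enters the formula.

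**4. How far a titre gap moves seroconversion.** For log-normal titres, P(VNA ≥ 0.5) = Φ[(log10 GMT - log10 0.5)/SD]. With an assumed RABAVERT GMT of 10 IU/mL and SD 0.4, this is 99.9% at GMT 10, 99.4% at 5 (2-fold lower) and 98.0% at 3.3 (3-fold lower). A 3-fold gap moves the rate by about 2 points; at SD 0.6 it moves it by 7 (98.5% to 91.5%).

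**5. What a GMT ratio would give on the same samples.** The CI factor is 10^[t × SD × √(1/n1 + 1/n2)] with n1+n2-2 df. For 14 vs 12 and SD 0.3: 10^(2.064 × 0.3 × 0.3934) = 10^0.2436 = 1.75. Power is from the noncentral t, two-sided 5%.

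| Pair | SD (log10) | CI: ratio ×/÷ | Power, 2-fold | Power, 3-fold |
|---|---|---|---|---|
| A or B vs D (14 vs 12) | 0.3 / 0.4 / 0.5 / 0.6 | 1.75 / 2.11 / 2.55 / 3.07 | 69 / 45 / 31 / 23% | 97 / 83 / 64 / 49% |
| C vs D (10 vs 12) | same | 1.85 / 2.28 / 2.80 / 3.43 | 61 / 39 / 27 / 20% | 94 / 75 / 56 / 42% |
| B vs C (14 vs 10) | same | 1.81 / 2.21 / 2.69 / 3.27 | 64 / 41 / 28 / 21% | 96 / 79 / 60 / 45% |

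**The case against.** The strongest reply is that little is actually lost. Table 21 prints GMTs with CIs side by side for every arm, visit and peak; the figures show the full distributions; Listing 9 gives each titre. A regimen at one third of RABAVERT's GMT would be visible, and because the CIs are t-based a reader could back out the SDs and compute a ratio, apart from rounding. The secondary objective is an assessment in each group, and comparing durability is exploratory. SAP 5 says: "This trial was not designed to formally test any hypotheses associated with the immunogenicity data". Protocol 11.1 says the trial "is exploratory rather than confirmatory, and was not designed to test a formal null hypothesis".

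Most of this stands, and it rules out stronger readings that a reader might infer:

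- *That arms are compared only on seroconversion, or that one versus two doses has no analysis at all.* Not supported. The exploratory models include vaccine type, dosage and number of doses. Their weakness is that the titre model's status differs between documents and its output is unspecified.
- *That seroconversion will be about 100% in every arm and visit.* Not supported. The statement concerns a completed licensed series, and the ChAd155-RG evidence is from macaques. RABAVERT's last dose follows the Day 22 sample, so Days 8, 15 and 22 precede completion, and Day 381 is about a year out. The contrast does respond away from the ceiling. For a 3-fold lower titre (14 vs 12, SD 0.3 to 0.5), the planned interval excludes zero in 16 to 29% of trials at an assumed RABAVERT GMT of 3 IU/mL, 36 to 61% at 2, and 43 to 75% at 1.5.
- *That the trial cannot show a titre difference.* Not supported, given the arm-level displays.

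What the reply does not remove: no output gives an interval for a between-arm titre difference, and the missing row contradicts the SAP's own text. Being exploratory rules out formal tests, not estimates. The SAP already reports unadjusted pair-wise intervals on the less informative scale.

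**Conclusion.** The point holds as a limit of the committed contrasts, not of the trial. The only between-arm VNA interval the plan commits to is on seroconversion, and with both arms at 100% it is fixed by the group sizes alone (-22 to +25 points for 14 vs 12). Between-arm titre comparison rests on an exploratory model that is firm in the protocol, optional in the SAP, and open in its output. Table 23's omission of High Dose (x1) vs (x2) is a text-versus-table inconsistency that depends on no assumption.

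The size of the gain does rest on an assumption, the titre SD. Over 0.3 to 0.6 log10, a GMT ratio has good power for a 3-fold difference from RABAVERT only at the lower SDs (83% or more for A or B vs D at SD 0.4 or below). It reaches at most 69% for 2-fold, so the benefit is an honest interval and not assured detection of 2-fold. This is a cheap improvement.

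**What to change.** In SAP Tables 23 and 24, with matching text in 8.2.1:

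1. Add GMT ratios with 95% CIs (difference in mean log10 titre, t interval, back-transformed) for each ChAd155-RG arm vs RABAVERT at each post-vaccination visit and at peak.
2. Add the same ratio for High Dose (x2) vs (x1) from Day 22 onward. The two groups are treated identically up to the Day 15 pre-dose sample, and the shells already pool them until then.
3. Add the High Dose (x1) vs (x2) row to the seroconversion differences, also from Day 22.
4. Make the protocol and SAP agree on whether the log-titre regression will be done.
5. Label all of these descriptive and unadjusted, consistent with SAP 6.8. Add a footnote that early-visit ratios may depend on setting values below the LLOQ to 0.05 IU/mL.

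The cost is one block and one row in two existing tables. No new samples or subjects are needed. The downside is more unadjusted intervals in a descriptive trial.
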